6.0 Laboratory Studies

These studies will be performed at Creatv Microtech. The outcomes of the study are determination of the prevalence, positive and negative predictive value of CAMLs in pulmonary nodules.

7.0 Study Calendar

Study	Enrollment	Scan 2 ¹	Scan 3 ¹	Biopsy or other diagnostic/therapeutic procedure ¹	Follow up
Informed consent	x				
Medical History	x			x	
Physical exam	x				
Smoking history	x				

Occupational and other exposures	x				
Medications	x				
PFTs ¹	x				
CT chest	x				x
CT/PET or PET ¹					x
CAML	x			x	
Nodule(s) measurement	x	x	x	x	x
Nodule characteristics	x	x	x	x	x

¹ If clinically indicated

8.0 Measurement of Lung Nodules

Bidimensional measurements of lung nodules will be performed. Measurements may be done by radiologist or pulmonary physician from CT scans with 5 mm (or less) cuts, using lung windows in the axial plane.

9.0 Statistical Considerations

Aim 1: Demographic and clinical characteristics of the study population will be summarized using standard methods (e.g., means, standard deviations, medians, binomial proportions, frequencies, two-sided confidence intervals). The proportion of patients with presence of CAMLs (CAML+) at the initial screen, with 95% two-sided confidence intervals, will be tabulated for the entire population. These statistics will also be used to summarize the presence of CAMLs at the time of an invasive follow-up procedure. The concordance of CAML results measured at two time points within the same individual will be evaluated using Cohen's Kappa.

Aim 2: Positive Predictive Value (PPV), Negative Predictive Value (NPV), sensitivity and specificity of CAMLs at the initial screen (along with two-sided 95% confidence intervals (CI)) will be computed for the entire study population. Patients with biopsy confirmed lung cancer during the entire duration of the study since initial CAML test will be defined as “diseased”; otherwise, they will be deemed “disease free”. We conservatively estimate that we will be able to accrue 1,000 patients with pulmonary nodules. We anticipate that ~35 and ~965 patients will be CAML+ CAML- at the initial screen, respectively. The expected accuracy of PPV and NPV estimates are presented in table 1.

Table 1. Accuracy of PPV and NPV estimates.

PPV or NPV estimate	Two-sided 95% CI for PPV	Two-sided 95% CI for NPV
0.5	±0.166	±0.032
0.7	±0.152	±0.029

0.9	±0.099	±0.019
-----	--------	--------

Aim 3: We will use logistic regression models to assess the utility of presence/absence of CAMLs after accounting for clinical factors and nodule characteristics. The primary analysis will be at the patient level, since this approach is most consistent with the potential future application of a validated CAML test in the clinic. The dependent variable will be a binary indicator of patient disease status as described for Aim 2 (1=diseased, 0=disease free). Independent variables will include presence/absence of CAMLs as well as factors previously identified in the literature as important predictors of lung cancer status including age, gender, smoking status, lesion diameter, spiculation, family history of lung cancer, emphysema, clear borders, and exposure to asbestos or other common pulmonary carcinogens.^{xv xvi xvii} When more than one lesion is detected in the same patient, lesion-specific covariate values (e.g., nodule diameter, spiculation) for that patient will be based on the nodule with highest risk of lung cancer. Continuous covariates may be modelled using restricted cubic splines to account for non-linear effects. As recommended by Pepe et al, Seshan et al and Vickers et al, the significance of the association between CAML test results and cancer status controlling for previously established clinical and radiological characteristics will be assessed using a Wald statistic from the multivariable logistic regression model (two-sided, 5% type I error).^{xviii xix} Table 2 displays detectable differences between CAML+ and CAML- patients from these multivariable^{xx}models, under a number of conditions.^{xxi} These estimates assume data are available from 1,000 patients with suspicious nodules (35 CAML+ and 965 CAML-), and approximately 3.5% of patients will subsequently have biopsy-confirmed lung cancer.

Table 2. Detectable differences in proportion with lung cancer between CAML+ and CAML – patients.

Squared multiple correlation between CAML status and other independent variables in the model	Detectable difference in the proportion with lung cancer between CAML+ and CAML – patients	Power
0.0	0.111	80%
0.1	0.118	80%
0.2	0.127	80%
0.3	0.138	80%

Table 3. Two-sided 95% confidence intervals for varied AUCs

AUC	Lower Bound	Upper Bound
0.80	0.71	0.89
0.85	0.77	0.93
0.90	0.83	0.97

0.95	0.90	1.00
------	------	------

Receiver Operating Characteristic (ROC) curves and area under the ROC curve (AUC), with associated 95% two-sided confidence intervals, will be created to summarize the predictive accuracy of the model. Given the anticipated sample size, the upper and lower bounds for 95% two-sided confidence intervals for a range of possible AUCs are presented in Table 3.^{xxii} In addition, the performance of the model will be evaluated using leave-one-out cross validation.

In secondary analyses, we will test second-order interactions between presence/absence of CAMLs and other covariates to explore whether test performance differs among subsets of the population defined by demographic, clinical and nodule characteristics.

In exploratory analyses we will conduct nodule-specific analyses using methods similar to those described above. In this case, the dependent variable will be a binary indicator of nodule disease status (1=cancer detected, 0=cancer not detected). To account for the fact that some subjects may have multiple nodules, the logistic models will be fit using generalized estimating equation methods (GEE) (and robust variance estimates will be used for inference.^{xxiii} The power estimates in Table 2 are based on the assumption that there will be only 1 nodule per patient. Given that some subjects will have multiple nodules, the actual power of these exploratory analyses will likely exceed the stated estimates.

We will also evaluate the value of adding CAMLs to previously defined algorithms for evaluation of pulmonary nodules and the ability of CAMLs to potentially replace other known variables.

Trial feasibility: The trial calls for a total of 1000 evaluable patients accrued over 2 years. To assess the feasibility of this accrual rate, we examined the number of potentially eligible patients seen in the FCCC pulmonary clinic for FY 2017 (7/1/2016 to 6/30/2017). We found that there were over 1200 patients referred for evaluation of pulmonary nodules. The exact size of these nodules has not been captured in the data base, but the majority are within the indeterminate range. At the VA Philadelphia, the pulmonary nodule clinic performs over 1500 bronchoscopies/year and sees over 200 patients/year with pulmonary nodules measuring .8-3.0 cm. Therefore, between the two institutions, we feel confident that we will be able to enroll 1000 patients with indeterminate nodules within 24 months of activation.

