5.0 Study Plan

5.1 Duration of study

The study duration is anticipated to be three years. Patients would be registered during the first 2 years and followed for a maximum of 3 years since the beginning of the study. Patient who is registered towards the end of 2nd year will be followed for 12 months, i.e, end of the study.

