5.2 Duration of Follow up

Patients will be in the study from the time of enrollment until the follow up. Follow up is the time when a CT scan and nodule assessment is done after the biopsy. Patients will be followed for a minimum of one year from accrual (last patient accrued) to a maximum of three years (patient accrued at the beginning of study).

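### Disease status is read over 12 to 36 months depending only on entry date, so the accuracy measures and the Aim 3 outcome mix follow-up horizons

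*Combined protocol and SAP*

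**What the plan says.** Section 9.0, Aim 2 calls a patient diseased if lung cancer is biopsy-confirmed "during the entire duration of the study since initial CAML test". For all others, "otherwise, they will be deemed" disease free. No minimum follow-up is attached to that default, and no rule covers withdrawal or death.

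The window comes from Section 5. Section 5.1 states "The study duration is anticipated to be three years", with registration in the first two years, and adds: "Patient who is registered towards the end of 2nd year will be followed for 12 months". Section 5.2 says patients are "followed for a minimum of one year from accrual (last patient accrued) to a maximum of three years". The same section also keeps patients in the study until follow-up, which it defines thus: "Follow up is the time when a CT scan and nodule assessment is done after the biopsy".

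Aim 3 uses the same outcome: "The dependent variable will be a binary indicator of patient disease status as described for Aim 2". Its listed covariates do not include length of follow-up. The 3.5% cancer proportion used for planning in Aim 3 carries no time point.

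**The concern.** Two patients with the same nodule, the same baseline CAML result and the same diagnosis at month 20 are classified differently according to when they enrolled. If CAML-negative, the early enrollee is a missed cancer and the late one a true negative. If CAML-positive, the early enrollee is a true positive and the late one a false positive. All four accuracy measures are affected.

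The plan gives reason to expect some late confirmations. Work-up follows ordinary care (Section 3.1), the calendar allows two further scans and a biopsy when clinically indicated (Section 7.0), and Section 1.1 describes nodule evaluation as relying on continued follow-up.

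At stake is interpretation. A reported NPV could not be read as freedom from cancer for any stated period. The estimates would also shift with the accrual pattern even if the test did not change.

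**Working it through.** **The plan's own figures.** Follow-up = 36 − entry month, with entry from month 0 to 24. The first patient has 36 − 0 = 36 months and the last 36 − 24 = 12, which matches Sections 5.1 and 5.2. Under uniform accrual (an assumption) the mean is 24 months, and the share reaching month t is (36 − t)/24: 75% reach 18 months, 50% reach 24, 25% reach 30.

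Tables 1 to 3 reproduce from their inputs. Table 1 is exact (for example 1.96 × √(0.5 × 0.5/35) = 0.166). Table 2 gives 0.112, 0.119, 0.128 and 0.138 against the printed 0.111, 0.118, 0.127 and 0.138. Table 3 agrees to two decimals. The issue is the outcome definition, not the arithmetic.

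**How many counted cancers depend on entry date.** Assumptions not in the documents: 3.0% confirmed by month 12, then h per year, with uniform accrual. Risk at f years = 3.0% + h(f − 1). Mean f is 2, so the pooled risk is 3.0% + h and the first patient's risk is 3.0% + 2h.

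| h per year | Last patient | First patient | Ratio | Pooled | Share after month 12 |
|---|---|---|---|---|---|
| 0.25% | 3.0% | 3.5% | 1.17 | 3.25% | 0.25/3.25 = 8% |
| 0.5% | 3.0% | 4.0% | 1.33 | 3.5% | 0.5/3.5 = 14% |
| 1.0% | 3.0% | 5.0% | 1.67 | 4.0% | 1.0/4.0 = 25% |

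The middle row averages to the plan's 3.5%.

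**Sensitivity.** Pooled sensitivity = 0.63 − (late share) × (0.63 − s). Here 0.63 is the pilot Stage I positivity (Section 1.1), used for early-confirmed cancers, and s is the unknown value for late-confirmed ones.

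| Late share | s = 0.63 | s = 0.30 | s = 0.18 |
|---|---|---|---|
| 8% | 0.63 | 0.60 | 0.60 |
| 14% | 0.63 | 0.58 | 0.57 |
| 25% | 0.63 | 0.55 | 0.52 |

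With equal positivity there is no shift.

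**The other measures.** These move even with equal positivity. Take the middle row, sensitivity 0.63 throughout, and the plan's 35 CAML-positive and 965 CAML-negative patients. If all 1,000 were read at 12, 24 or 36 months:

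| Horizon | Cancers | True positives | PPV | NPV | Specificity |
|---|---|---|---|---|---|
| 12 | 30 | 18.9 | 18.9/35 = 0.54 | 1 − 11.1/965 = 0.989 | 1 − 16.1/970 = 0.983 |
| 24 | 35 | 22.05 | 22.05/35 = 0.63 | 1 − 12.95/965 = 0.987 | 1 − 12.95/965 = 0.987 |
| 36 | 40 | 25.2 | 25.2/35 = 0.72 | 1 − 14.8/965 = 0.985 | 1 − 9.8/960 = 0.990 |

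Under these assumptions the any-time table would land on the 24-month row, although half the patients would not have been observed that long. PPV is the measure most exposed. Its half-width at 0.63 is 1.96 × √(0.63 × 0.37/35) = 0.16.

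**The case against.** The strongest reply is that the target is cancer already present in the nodule. Section 1.2 frames CAMLs as enriching for malignancy in people who have nodules, and Section 4.1 requires a nodule not yet biopsied. On that reading longer follow-up is better verification, and a strict 12-month cut-off would score a baseline nodule proven malignant at month 18 as disease free. This stands as a reason to keep the any-time table and not make 12 months the sole outcome. It does not remove the problem, because verification would still be unequal by entry date and early withdrawals would still count as verified negatives.

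The shifts are also modest beside sampling error. In the middle case NPV moves by about 0.002 per year, against a half-width of about 0.007 (1.96 × √(0.987 × 0.013/965)). That stands too.

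A reader might infer more than the documents support:

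- **That sensitivity falls from 63% to 57%.** This needs late-confirmed cancers to be CAML-positive at only 18%, the pilot rate in benign disease. Nothing in the plan fixes that value.
- **That Aim 3 is confounded by site.** Site is not a listed covariate. Sites enrolling at different steady speeds over the same 24 months have the same follow-up distribution, so different timing would be needed.
- **That the CAML Wald test is invalid.** The documents give no link between entry date and CAML status.
- **That Section 5.2 ends observation soon after a benign biopsy.** The same section states a one-year minimum, and Section 5.3 does not list the post-biopsy CT as a removal criterion. This is loose wording, which also leaves never-biopsied patients without a defined follow-up point.

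**Conclusion.** The concern holds as a gap in the outcome definition. The planned window is 12 to 36 months, set only by entry date, with no horizon, no censoring and a disease-free default for patients lost early. That much comes directly from Sections 5.1, 5.2 and 9.0.

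The numerical size is not known. The ranges of 8% to 25% of counted cancers and 1.17 to 1.67 for the first-to-last risk ratio rest on assumed confirmation rates and uniform accrual. Both shrink towards no effect if nearly all cancers are confirmed by month 12. Sensitivity moves only if CAML positivity differs between early- and late-confirmed cancers. Even where the numbers barely move, the reported predictive values would lack a stated time frame.

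**What to change.** 1. In Section 9.0, Aim 2, keep the any-time table and label it as based on 12 to 36 months of planned follow-up.
2. Add cumulative incidence of biopsy-confirmed lung cancer by CAML status from the initial draw, with withdrawals censored and a stated rule for deaths. Report PPV (incidence in CAML-positive patients) and NPV (one minus incidence in CAML-negative patients) at 12 and 24 months. The 24-month values will be less precise: under uniform accrual half of patients reach that point, or about 17 of the 35 expected CAML-positives.
3. Repeat the Aim 2 table and the Aim 3 model with status at a fixed 12 months as a stated sensitivity analysis. Report patients last known cancer-free before month 12 separately, not as disease free.
4. Record the diagnosis date and the date of last known status. The biopsy block of the Follow Up Form has the result and type but no date.
5. In Section 5.2, reconcile the sentence defining follow-up as the post-biopsy CT with the one-year minimum, so that outcome collection by chart review continues to at least 12 months.
6. State the horizon to which the 3.5% planning value refers.

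The cost is some analysis work and two date fields, with no extra visits. Fixed-window intervals are somewhat wider: for a sensitivity of 0.63, 1.96 × √(0.63 × 0.37/n) is 0.17 with 30 cancers against 0.16 with 35. If only half of 35 cancers were confirmed by month 12 (17.5), it would be 0.23, which is a further reason to keep the 12-month version as a sensitivity analysis.

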1.0 Introduction

1.1 Background and Hypothesis

Lung cancer screening

[figure not shown]
Lung cancer remains the major cause of cancer related death in the United States, with over 220,000 cases detected and 180,000 deaths.ⁱ The National Lung Screening Trial (NLST), for which the PI was a member of the endpoint verification committee, determined that low dose CT screening could decrease lung cancer death by 20% compared with CXR and is now recommended by all major professional groups and US Preventative Services Task Force.ⁱⁱ However, there are several problems with the current screening paradigm. Most critically, over 39% of screened subjects were determined to have positive screens with only 96.4% false positive. This very high false positive rate results in several critical problems including the requirement for further testing (scans, biopsies), the potential of loss to follow-up, the possibility of false negative biopsy and the resultant patient stress and anxiety. While lung nodules <0.8 cm are considered low-risk findings and nodules >3.0 cm high-risk, nodules between from 0.8-3.0 cm have been described as “indeterminate” and represent a management challenge.ⁱⁱⁱ Therefore, there is a substantial need for a method to enrich the population of patients identified as likely to have malignancy and exclude those who have nodules not likely to have malignancy. The ideal test should be demonstrated to have high specificity and sensitivity. This is particularly important for patients with nodules of indeterminate size.

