Further, the study PI and co-PI performed a blinded preliminary comparison of 56 newly diagnosed **lung cancer patients**, 16 patients with benign conditions, and 40 healthy controls (FIG 5). Sensitivity of this study showed the number of patients (% positive): Stage I (63%), Stage II (86%), Stage III (92%), Stage IV 100%, unknown stage (100%); while the benign lung disease (18%) and healthy controls (0%). For malignant versus benign lung disease AUC=0.85, and for invasive versus health controls AUC=0.92. The current proposal will extend the above data to evaluate the prevalence and potential utility of CAMLS in individuals with pulmonary nodules to determine their use as a surrogate biomarker for cancerous nodules.

The prevalence and specificity of CAMLS in malignant disease is believed to be caused by immune inflammation and the specific microenvironment formed in cancerous and pre-cancerous lesions. Typically giant polyploidy cells, like CAMLS, derive from common MPCs by either means of a pre-specified cascade of cellular differentiation (i.e. megakaryocytes or kupffer cells) or by an inflammatory response causing cell to cell fusion with nearby cells (Langhans or Foreign-body giant cells). Within the solid tumor mass, the commonly seen giant cancer associated polyploid cells are presumed to be caused by an aberrant inflammatory response caused during malignant growth, and the likely origin of CAMLS prior to dissemination into circulation. Further, because tumor derived giant polyploids are found in most early solid tumors, can negatively correlate with survival, and accumulate in pre-metastatic disease; it should be of little surprise that CAMLS in the blood

would have parallel clinical correlations. Additionally, while CTCs can act as a blood based surrogate to the tumor itself, CAMLs appear to act as a surrogate to the stromal microenvironment. Because stroma/immune inflammation is often larger than the tumor itself, and stromal genesis begins in both pre-cancerous and cancerous environments, it is not surprising that CAMLs would appear earlier and more commonly than actual CTCs.

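### Table 1's NPV rows cannot occur at the plan's own 3.5% cancer proportion, and the count of 35 CAML+ patients has no stated basis

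*Combined protocol and SAP*

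**What the plan says.** All planning figures are in section 9.0.

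- **Aim 2** states that PPV, NPV, sensitivity and specificity at the initial screen "will be computed for the entire study population". It plans on 1,000 patients and adds: "We anticipate that ~35 and ~965 patients will be CAML+ CAML- at the initial screen, respectively".
- **Table 1**, titled "Table 1. Accuracy of PPV and NPV estimates", has one shared column, "PPV or NPV estimate", with rows 0.5, 0.7 and 0.9. The half-widths are ±0.166, ±0.152 and ±0.099 for PPV, and ±0.032, ±0.029 and ±0.019 for NPV. The text introduces them as the accuracy to be expected.
- **Aim 3** keeps the Aim 2 definition of disease, repeats the 35/965 split as the basis of Table 2, and assumes that "approximately 3.5% of patients will subsequently have biopsy-confirmed lung cancer".

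Section 9.0 gives no source for the split. The lung pilot in section 1.1 reports CAML positivity as "Stage I (63%), Stage II (86%), Stage III (92%), Stage IV 100%, unknown stage (100%); while the benign lung disease (18"%), with 16 patients in the benign group and 0% positive among 40 healthy controls.

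**The concern.** Two separate inputs need attention.

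**NPV rows.** A low NPV needs many cancers among the CAML- patients. The plan expects 35 cancers in the whole cohort, so rows of 0.5 to 0.9 at 965 CAML- patients look unreachable. If they are, the table says nothing useful about the precision of a secondary endpoint.

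**CAML+ count.** The 35 CAML+ equals the 35 expected cancers and is not derived. It sets the PPV column of Table 1 and all of Table 2. It also implies an expected value of 3.5% for CAML prevalence, the primary objective in section 2.1. A very different count would make the precision and detectable differences shown in advance a poor guide to what the study will deliver.

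**Working it through.** **Inputs.** N = 1,000; 35 CAML+ and 965 CAML- (Aims 2 and 3); 35 cancers (3.5%, Aim 3); two-sided 95% intervals; pilot positivity of 63-100% in cancer and 18% in benign disease (section 1.1).

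**1. Reproducing the plan's tables.** The Table 1 half-width is 1.96·√(p(1−p)/n).

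| p | n = 35 | n = 965 |
|---|---|---|
| 0.5 | 0.166 | 0.0315 |
| 0.7 | 0.152 | 0.0289 |
| 0.9 | 0.099 | 0.0189 |

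These agree with Table 1. Table 2 is reproduced to within 0.001 by the Hsieh formula for a binary covariate with 35 CAML+, an overall cancer proportion of 0.035 and 80% power: 0.112, 0.119, 0.128 and 0.138, against the printed 0.111, 0.118, 0.127 and 0.138. Table 3 is reproduced by the Hanley-McNeil formula with 35 cancers and 965 non-cancers.

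**2. Lowest possible NPV.** If every cancer were CAML-, NPV = (965 − 35)/965 = 930/965 = 0.964. The half-width there is 1.96·√(0.9637·0.0363/965) = 0.0118, and it shrinks as NPV rises. The stated widths are 0.0189/0.0118 = 1.6 to 0.0315/0.0118 = 2.7 times too wide.

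Cancers needed among the CAML- patients are 965·(1 − NPV): 482.5 at NPV 0.5, 289.5 at 0.7 and 96.5 at 0.9. Even the 0.9 row needs a cancer proportion of at least 96.5/1,000 = 9.65%.

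The plan's margins also tie NPV to PPV. At 35 CAML+, PPV of 0.5, 0.7 and 0.9 leaves 17.5, 10.5 and 3.5 cancers among the 965, so NPV is 0.982, 0.989 and 0.996.

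**3. Would another CAML+ count repair the NPV rows?** No. At 804 CAML- the floor is 769/804 = 0.956. The 3.5% drives the problem, not the 35.

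**4. CAML+ count on the pilot rates.** Expected CAML+ = 35·sensitivity + 965·benign positivity.

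| Sensitivity | Benign positivity | CAML+ | PPV (half-width) |
|---|---|---|---|
| 63% | 18% | 22.05 + 173.7 = 195.8 | 0.113 (±0.044) |
| 100% | 18% | 35 + 173.7 = 208.7 | 0.168 (±0.051) |

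To reach 35 CAML+, benign positivity must be (35 − 22.05)/965 = 1.3% at 63% sensitivity, or 0% at 100%.

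Reading 18% as 3 of 16 is an assumption (3/16 = 18.75%). It gives exact 95% limits of 4.0% to 45.6%, and a CAML+ count from 61 (63% sensitivity, lower limit) to 476 (100%, upper limit).

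**5. Effect on Table 2.** By the same Hsieh formula at R² = 0, the detectable difference is about 0.112 at 35 CAML+, 0.082 at 61 and 0.045 at 196. At 196 CAML+ (63% sensitivity, 18% benign positivity) the implied difference in cancer proportion is 0.097. Power is then 99.8% at R² = 0 and 98.8% at R² = 0.3.

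**The case against.** **The rows are generic.** Table 1 applies one scenario grid to PPV and NPV, and the plan nowhere predicts an NPV of 0.5. The error is also conservative. Both points are fair and limit the consequence. They do not rescue the NPV column, because no row in it is attainable on the plan's own figures.

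**Table 1 might be meant for biopsied patients**, the group named in section 2.2, where cancer would presumably be more common. Aim 2 says otherwise, and 965 is a count for the whole cohort.

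**The pilot is a weak benchmark.** This stands. The benign group has 16 patients and is not described as having nodules of 0.8-3.0 cm. Section 1.1 calls CAMLs rare with benign masses, sections 4.1 and 4.2 exclude several inflammatory conditions, and some figures are missing from the readable text. Benign positivity in the trial may be well below 18%. A reader might infer that 35 is contradicted by the protocol's own data. The documents do not support that, only that 35 lacks a stated basis.

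**A copied figure?** A reader might also infer that the cancer proportion was carried over as the CAML+ proportion. Section 1.1 does describe "positive screens with only 96.4% false positive", which leaves 3.6% true positives, but that is a cancer proportion and the plan does not say it is the source.

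**PPV rows.** By symmetry the 0.9 and 0.7 rows also give the half-width for PPV 0.1 and 0.3. That holds only at n = 35.

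**Conclusion.** **NPV rows: wrong as written, with high confidence.** This rests only on the plan's 1,000 patients, 965 CAML-, 3.5% cancers and whole-population definition. NPV must be at least 0.964 with a half-width of at most ±0.012. The printed values are 1.6 to 2.7 times too wide.

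**35 CAML+: unsupported input, with moderate confidence.** On the pilot rates the count would be about 196-209 and the PPV about 0.11-0.17. Even the lower exact limit of the assumed 3/16 gives about 61. The limits of the pilot keep this short of a contradiction.

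A reader might go further and conclude that the tables are miscalculated, that the study is too small, or that its stated power is wrong. None of these follows. Tables 1 to 3 are right for their inputs. The sample size rests on feasible accrual, and the final intervals will use observed counts. Table 2 becomes more favourable at about 196 CAML+, and power is ample on the pilot inputs. Table 3 does not depend on the CAML split.

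**What to change.** 1. Replace the NPV rows with attainable values, for example 0.97, 0.98 and 0.99 at n = 965 (±0.011, ±0.009, ±0.006). Alternatively, state a higher cancer proportion with its basis and use it consistently in Tables 1 to 3.
2. Derive the CAML+ count from a stated sensitivity, benign positivity and cancer proportion, with a range. If the exclusions are expected to lower benign positivity below the pilot's 18%, give the value and its basis.
3. Add PPV rows at the resulting count. At n = 196, for example, PPV of 0.05, 0.10, 0.15 and 0.20 has half-widths of ±0.031, ±0.042, ±0.050 and ±0.056.
4. Rerun Table 2 over the same range of CAML+ counts.

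The cost is a revision of the section 9.0 text and two recomputed tables, plus Table 3 if the cancer proportion changes. There are no added patients and no change of estimator or test. The downside is that the anticipated PPV becomes less favourable: about 0.11-0.17 on pilot inputs, against printed rows of 0.5 to 0.9.

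### Table 1 gives Wald half-widths that fall short of 95% coverage at PPV 0.7 and 0.9, its NPV rows are unattainable, and the plan names no interval method for the analysis

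*Combined protocol and SAP*

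**What the plan says.** The relevant text is in Section 9.0, Statistical Considerations.

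- **Estimates.** Aim 2 covers PPV, NPV, sensitivity and "specificity of CAMLs at the initial screen (along with two-sided 95% confidence intervals (CI)) will be computed for the entire study population". Aim 1 also promises two-sided 95% intervals for the proportion who are CAML-positive.
- **Denominators.** "We conservatively estimate that we will be able to accrue 1,000 patients with pulmonary nodules", and "We anticipate that ~35 and ~965 patients will be CAML+ CAML- at the initial screen, respectively".
- **Cancers.** Under Aim 3 the plan assumes that "approximately 3.5% of patients will subsequently have biopsy-confirmed lung cancer", which is about 35 of 1,000.
- **Table 1.** "The expected accuracy of PPV and NPV estimates are presented in table 1". At estimates of 0.5, 0.7 and 0.9, the column headed "Two-sided 95% CI for PPV" shows ±0.166, ±0.152 and ±0.099. The NPV column shows ±0.032, ±0.029 and ±0.019.

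Neither the table nor the text names a method for these intervals. Wald is mentioned only for the test statistic in the Aim 3 logistic model.

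**The concern.** Symmetric ± limits on 35 patients suggest a normal approximation, which is unreliable when a proportion is far from one half and the denominator is small. It is also unreliable on a large denominator when the proportion is very close to 1, which is where NPV must lie at 3.5% prevalence. Table 1 is the plan's only statement of precision for Aim 2. A reader would take from it that a PPV of 0.9 is known to lie between 0.80 and 1.00 with 95% confidence, and that NPVs of 0.5 to 0.9 are realistic outcomes.

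The schema names sensitivity and specificity as the primary endpoint, and Section 2.2 makes PPV and NPV a secondary objective. If the method behind Table 1 were carried into the analysis, some of these intervals would have less than the stated confidence.

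**Working it through.** **Inputs.** Two-sided 95%, z = 1.96; N = 1,000; 35 CAML-positive and 965 CAML-negative (Aim 2); 3.5% prevalence, so about 35 cancers (Aim 3).

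**Step 1: reproduce Table 1.** Wald half-width = 1.96 × √(p(1−p)/n).

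| p | n = 35 | Table 1 PPV | n = 965 | Table 1 NPV |
|---|---|---|---|---|
| 0.5 | 1.96 × √(0.25/35) = 0.1656 | 0.166 | 1.96 × √(0.25/965) = 0.03155 | 0.032 |
| 0.7 | 1.96 × √(0.21/35) = 0.1518 | 0.152 | 1.96 × √(0.21/965) = 0.0289 | 0.029 |
| 0.9 | 1.96 × √(0.09/35) = 0.0994 | 0.099 | 1.96 × √(0.09/965) = 0.0189 | 0.019 |

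All six agree. The PPV column separates the methods: half-widths at 0.5, 0.7 and 0.9 would be 0.180, 0.166 and 0.114 for Wald with continuity correction, 0.157, 0.146 and 0.102 for Wilson, and 0.173, 0.160 and 0.112 for Clopper-Pearson.

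**Step 2: coverage on 35 patients.** Coverage is the sum of Binomial(n, p) probabilities over every count whose interval contains p.

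| True PPV | Wald | Wilson | Clopper-Pearson |
|---|---|---|---|
| 0.5 | 95.9% | 95.9% | 95.9% |
| 0.7 | 91.9% | 93.7% | 97.5% |
| 0.9 | 87.1% | 92.0% | 98.0% |

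Averaged over PPV 0.5 to 0.9, Wald covers about 92.8% and Wilson about 95.1%. If the CAML-positive count varies as Binomial(1000, 0.035), Wald coverage at the three values is 93.9%, 93.2% and 88.8%. As an example of a single result, 32 of 35 gives a Wald interval of 0.822 to 1.007, against 0.776 to 0.970 by Wilson.

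Low PPVs are affected too. Table 2's detectable difference of 0.111 at 3.5% prevalence implies a PPV of 0.035 + 0.965 × 0.111 = 0.142, where Wald covers 88.4%.

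Sensitivity has about the same denominator. At 0.63, the Stage I positivity quoted in Section 1.1, Wald covers 91.6% and Wilson 94.8%.

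**Step 3: which NPVs can occur.** At most 35 of the 965 CAML-negative patients can have cancer, so NPV ≥ (965 − 35)/965 = 930/965 = 0.964. Even the 0.9 row would need 0.1 × 965 = 96.5 cancers among CAML-negative patients, against 35 planned in the whole cohort.

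**Step 4: coverage on 965 patients.** At the printed rows, Wald covers 94.7%, 95.0% and 95.1%. At attainable values, NPV = 1 − 35(1 − PPV)/965:

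- PPV 0.5: 1 − 17.5/965 = 0.9819; Wald covers 92.2%.
- PPV 0.7: 1 − 10.5/965 = 0.9891; Wald covers 93.9%.
- PPV 0.9: 1 − 3.5/965 = 0.9964; Wald covers 86.1%.

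Coverage jumps between neighbouring values: it is 94.9% at 0.982 and 91.0% at 0.99. The mean over 0.964 to 0.999 is about 92.6% for Wald and 95.2% for Wilson. The limits barely differ: at 0.965, Wald gives 0.953 to 0.977 and Wilson 0.951 to 0.975; at 0.982, Wald gives 0.974 to 0.990 and Wilson 0.972 to 0.989.

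**The case against.** - **Table 1 is a planning table.** A normal approximation there is compatible with exact intervals at analysis. This stands. A reader might infer that the trial will report Wald intervals, but the documents do not say so. What they show is Wald planning figures and an unstated analysis method.
- **Most printed entries are sound on coverage.** A reader might infer that the whole of Table 1 under-covers. It does not: PPV 0.5 and all three NPV rows are at or close to nominal, so four of six entries are unaffected. Those three NPV rows, however, are the ones that cannot occur.
- **Wald is not simply too short.** At PPV 0.5 and 0.7 the Wilson half-widths are narrower than Wald (0.157 against 0.166; 0.146 against 0.152). The printed 0.9 row ends at 0.999 and does not pass 1, although individual results such as 32 of 35 would. Wilson also falls to 92.0% at PPV 0.9. All of this stands.
- **A PPV of 0.9 on 35 patients may not arise.** Section 1.1's preliminary rates (63% positive in Stage I, 18% in benign disease) would give 0.63 × 35 + 0.18 × 965 = about 196 CAML-positive patients and a PPV of 22/196 = about 0.11, where Wald covers about 94–95%. That would shrink the PPV problem. But 35 and 0.9 are the plan's own planning values, and sensitivity would still rest on about 35 cancers.
- **Nothing in the plan depends on Table 1.** No decision rule or sample size is derived from it. This limits the importance of the point but does not make the table right.

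**Conclusion.** The point holds in a limited form. Table 1 consists of Wald half-widths, and the plan leaves the analysis method for Aims 1 and 2 open. On 35 patients the stated 95% is really 91.9% at PPV 0.7 and 87.1% at 0.9; at 0.5 it is met. The NPV column is a separate planning error whatever the interval method, because all three rows lie below the floor of 0.964 set by the plan's own counts. At attainable NPVs the Wald shortfall is irregular, and its practical effect is small, at about 0.002 in the limits.

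These figures assume the plan's 35 CAML-positive patients and 35 cancers, and coverage is computed with the denominators fixed. Letting the CAML-positive count vary softens the PPV figures, to 88.8% at 0.9, without removing the shortfall. More cancers than planned would lower the NPV floor, but reaching 0.9 would take nearly three times the planned number. The matter should be corrected before analysis; it does not threaten the validity of the trial.

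**What to change.** 1. Add one sentence to Section 9.0 naming the interval method for all Aim 1 and Aim 2 proportions. Clopper-Pearson guarantees at least 95% coverage. Wilson averages about 95% but covers 92.0% at PPV 0.9 with n = 35.
2. Restate the PPV column of Table 1 (n = 35) with lower and upper limits:

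| PPV | Clopper-Pearson | Wilson |
|---|---|---|
| 0.5 | 0.33–0.67 | 0.34–0.66 |
| 0.7 | 0.52–0.84 | 0.53–0.83 |
| 0.9 | 0.75–0.98 | 0.76–0.96 |

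3. Replace the NPV rows with attainable values. By Wilson with n = 965: 0.965 (0.951–0.975), 0.982 (0.972–0.989) and 0.996 (0.990–0.998). If Clopper-Pearson is chosen, compute these rows by that method.
4. Add rows for sensitivity on about 35 cancers, using the same method.

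No extra patients or data are needed. Exact intervals are slightly wider, and the stated lower limit at PPV 0.9 drops from 0.80 to about 0.75.
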